### **Definition of serious adverse events (SAE)**

A serious adverse event (AE) or suspected adverse event/reaction is any untoward medical occurrence that at any dose, in the view of either the Principal Investigator or the Sponsor, it results in any of the following outcomes:

- **Death**
- **A life-threatening adverse event**

The term 'life-threatening' in the definition of 'serious' refers to an event in which the patient was at risk of death at the time of the event. It does not refer to an event, which hypothetically might have caused death, if it were more severe.

- **Inpatient hospitalization or prolongation of existing hospitalization**

In general, hospitalization signifies that the patient has been detained (usually involving at least an overnight stay) at the hospital or emergency ward for observation and/or treatment that would not have been appropriate in the physician's office or outpatient setting.

Complications that occur during hospitalization are AEs. If a complication prolongs hospitalization or fulfills any other serious criteria, the event is serious. When in doubt as to whether "hospitalization" occurred or was necessary, the AE should be considered serious.

Hospitalization for elective treatment of a pre-existing condition that did not worsen from baseline is not considered an AE.

Planned hospital stays would not be counted as SAEs, nor would stays in hospital for “social reasons” (e.g., respite care, the fact that there is no-one at home to care for the patient).

- A persistent or significant incapacity or substantial disruption of the ability to conduct normal life functions**

The term disability means a substantial disruption of a person’s ability to conduct normal life functions.

This definition is not intended to include experiences of relatively minor medical significance such as uncomplicated headache, nausea, vomiting, diarrhea, influenza, and accidental trauma (e.g., sprained ankle) which may interfere with or prevent everyday life functions but do not constitute a substantial disruption.

- A congenital anomaly/birth defect**
- Any medically significant events** that may not result in death, be life-threatening, or require hospitalization may be considered serious when, based upon appropriate medical judgment, they may jeopardize the patient and may require medical or surgical treatment to prevent one of the outcomes listed in this definition.

Examples of such events include, but are not limited to, potential Hy’s law, invasive or malignant cancers, intensive treatment in an emergency room or at home for allergic bronchospasm, blood dyscrasias or convulsions that do not result in hospitalization, or development of drug dependency or drug abuse

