### 3.2. Study endpoints

#### Primary Endpoint

Evaluation of all SAEs and NVDX3 related AEs between screening (V1) and 12-months post-IS (V8).

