#### **8.1.7. Adverse Events and Serious Adverse Events**

##### **Definition adverse events (AE)**

Adverse event means any untoward medical occurrence associated with the use of an intervention in humans, whether or not considered intervention-related

An AE is defined as any untoward medical occurrence in a patient or clinical investigation subject administered the NVDX3 therapy and which does not necessarily have to have a causal relationship with this treatment

Events meeting the AE definition:

- Any abnormal laboratory test results (hematology, clinical chemistry, or urinalysis) or other safety assessments (e.g., radiological acquisitions, vital signs measurements), including those

that worsen from baseline, considered clinically significant in the medical and scientific judgment of the Principal Investigator (e.g. not related to progression of underlying disease).

- Exacerbation of a chronic or intermittent pre-existing condition including either an increase in frequency and/or intensity of the condition.
- New conditions detected or diagnosed after trial treatment administration even though it may have been present before the start of the trial.
- Signs, symptoms, or the clinical sequelae of a suspected drug-drug interaction.

Events NOT meeting the AE definition:

- Any clinically significant abnormal laboratory findings or other abnormal safety assessments which are associated with the underlying disease, unless judged by the Principal Investigator to be more severe than expected for the patient's condition.
- The disease/disorder being studied or expected progression, signs, or symptoms of the disease/disorder being studied, unless more severe than expected for the patient's condition.
- Medical or surgical procedure (e.g. endoscopy, appendectomy): the condition that leads to the procedure is the AE.
- Situations in which an untoward medical occurrence did not occur (social and/or convenience admission to a hospital).
- Anticipated day-to-day fluctuations of pre-existing disease(s) or condition(s) present or detected at the start of the trial that do not worsen.
- Pregnancy

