## **AE of Special Interest (AESI)**

The following adverse events will be considered as of special interest:

- Hypersensitivity reaction
- Immunological reaction
- An AE requiring immunosuppressive medication
- Ectopic bone formation
- Tumor formation
- Treatment failure:
  - Continued non-union/Non-fusion
  - Refracture of the targeted area
  - Revision surgery/intervention including removal of NVD-X3
  - Any other condition considered by the treating physician as treatment failure

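### The SAE exemption for planned hospital stays has no limit of date or reason, so some scheduled admissions during the trial can fall outside the primary safety endpoint

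*Protocol*

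**What the plan says.** Protocol 8.1.7 (definition of serious adverse events) lists "Inpatient hospitalization or prolongation of existing hospitalization" among the outcomes that make an untoward medical occurrence serious. Two exemptions follow as separate sentences:

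- The first, on elective care, reads "Hospitalization for elective treatment of a pre-existing condition that did not worsen from baseline is not considered an AE".
- The second, which also exempts stays for social reasons, reads "Planned hospital stays would not be counted as SAEs".

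The first is limited to pre-existing conditions that have not worsened. The second carries no such limit and no planning date.

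The primary endpoint (Protocol 3.2, SAP 1.3.1) consists of all SAEs and all NVDX3-related AEs from screening to 12 months after implant surgery. SAP 2.4.1.4 does not treat an event as NVDX3-related when its cause is the grafting surgery or another study procedure. The AESI list in Protocol 8.1.7 includes "Revision surgery/intervention including removal of NVD-X3". An AESI becomes reportable on the SAE route only if the investigator rates it at least possibly related to NVDX3.

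**The concern.** An event enters the primary endpoint through seriousness or through attribution to NVDX3. In a single-arm, first-in-human study, attribution is a judgement made without a comparator, so the SAE count is the component that does not depend on it. Protocol 1.2.1 itself names tendon rupture, nerve injury, malunion, nonunion and loss of reduction as risks of the fracture surgery, so attributing such an event to surgery alone would be a natural choice. Once that is done, seriousness is the only way left into the primary endpoint.

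An exemption that turns on whether the admission was scheduled, and not on why the patient was admitted, weakens that way in. At stake are the completeness of the primary safety result, the serious-event outputs, and how quickly the sponsor hears of the event.

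**Working it through.** The plan gives no figure on this point, so the check is a comparison of texts, followed by tracing one hypothetical event.

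**Step 1: does anything else supply the missing limit?**

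- The preceding sentence already covers elective treatment of an unworsened pre-existing condition. If planned stays meant only those, the second exemption would add little beyond the index stay. Its wording is confined to neither.
- The tie-break in 8.1.7 ends "or was necessary, the AE should be considered serious". It settles doubt about whether a hospitalisation took place or was needed, not whether it was planned.
- Protocol 6.1.3 requires an SAE when an adverse event prolongs the index stay. It does not deal with readmission.
- The AE definition says of procedures that "the condition that leads to the procedure is the AE". This keeps the complication as an AE but does not make it serious.
- The readable SAP text, including the list of changes in SAP 3.6, adds no rule on planned stays. SAP 2.4.1 is partly blacked out, so nothing is inferred from its silence.

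**Step 2: trace one event.** Assume a patient is admitted by appointment during follow-up for a complication that arose after surgery. The investigator attributes it only to the surgery or the fixation. No other seriousness criterion is met, and the sponsor does not judge the event serious.

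| Output | Event included? | Source |
|---|---|---|
| SAE through hospitalisation | No, if the exemption is read literally | Protocol 8.1.7 |
| NVDX3-related AE | No | SAP 2.4.1.4 |
| Primary endpoint | No | Protocol 3.2; SAP 1.3.1 |
| Serious-TEAE overview and listing | No | SAP 4.4.1 |
| Reportable AESI | No | Protocol 8.1.7; SAP 2.4.1.5 |
| Report to the sponsor within 24 hours | No; eCRF entry within 5 working days instead | Protocol 8.2.5 and 8.2.4 |
| TEAE tables, and the overview line for surgery-related TEAEs | Yes | SAP 4.4.1 |
| AESI overview line and listing | Yes, if a revision or other treatment failure | SAP 2.4.1.5 and 4.4.1 |

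**Step 3: vary the assumptions.**

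- Rated at least possibly related to NVDX3, or causality missing: the event is NVDX3-related under SAP 2.4.1.4 and stays in the primary endpoint, serious or not.
- An AESI that the investigator rates at least possibly related to NVDX3: reportable, with 24-hour reporting kept.
- Incapacity criterion met: serious whether or not the stay was planned.
- Judged medically significant because "they may jeopardize the patient and may require medical or surgical treatment to prevent one of the outcomes listed in this definition": the event may be called serious, but this is discretionary.
- Sponsor considers it serious: Protocol 8.1.7 accepts the view of either the investigator or the sponsor.

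**Step 4: scale.** The planned number is 10 patients (Protocol 9.5). One uncounted patient is 1/10 = 10 percentage points of the proportion with an SAE. The documents give no rate of planned readmission or revision, so an expected number of lost events cannot be derived. The analysis is descriptive, and SAP 3.4 plans only counts and percentages for categorical data, so there is no planned interval or test to recompute.

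**The case against.** The strongest reply is that the sentence is ordinary safety-reporting language. It groups planned stays with social stays and follows the sentence on elective treatment, so its natural sense is that a stay in itself is not an adverse event. The trial also begins with a planned surgical stay that has to be exempted. The underlying complication remains an AE, and the incapacity criterion, the sponsor's own view and the inclusion of all NVDX3-related AEs each keep many events in the primary endpoint. Process detail sits in the Safety Monitoring Plan, which is not available here.

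Most of this stands, and it narrows the point. It does not remove it: the intended meaning is not written down, and someone following the sentence as it reads would exempt a scheduled admission for a new complication.

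A reader might infer more than the documents support:

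- *That every inpatient stay is an SAE, so 8.1.7 contradicts itself.* It does not. The criterion applies to an untoward occurrence that results in hospitalisation, and the exemption qualifies it. The fault is that the exemption has no boundary.
- *That admissions for failed treatment in general leave the primary endpoint.* Those rated NVDX3-related, or with causality missing, remain in it.
- *That the medically significant item is the only other route to seriousness.* The incapacity criterion and the sponsor's judgement also apply.
- *That late complications are mostly handled by scheduled admission, so the effect concentrates after week 6.* The documents say nothing on this.

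**Conclusion.** The point holds in a limited form. The exemption has no limit of time or reason, and nothing readable in the protocol or SAP supplies one. An event is lost to the primary endpoint only if five conditions all hold: the admission is scheduled, the exemption is read literally, the event is rated not related to NVDX3, no other seriousness criterion is met, and the sponsor does not judge it serious. Such an event also leaves the serious-TEAE outputs and 24-hour reporting.

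The data are not lost, because the event remains a TEAE and, where it is a revision or other treatment failure, an AESI. The harm is misclassification in the primary endpoint and slower notification. Its frequency is unknown; its unit is 1 patient in 10. No bias in the primary result is demonstrated, but the ambiguity should be removed because the SAE count is the attribution-free part of that result.

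**What to change.** Keep the existing sentence on elective treatment of an unworsened pre-existing condition. Limit the planned-stay exemption in Protocol 8.1.7, or in the Safety Monitoring Plan, with wording such as: *The stay for the index implant surgery, and stays planned before signature of the ICF for a pre-existing condition that has not worsened, are not SAEs. An admission for a condition that is new or has worsened after consent is assessed under the hospitalisation criterion even if it is scheduled.* The exemption for social stays can remain unchanged.

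At the data review before database lock, which SAP 3.2 already foresees, check the seriousness coding of every admission after the index discharge against this rule. Describe any resulting change in the analysis in the CSR, as the SAP introduction requires.

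This changes a reporting definition and does not affect patient management. The cost is one short text change, which needs review and approval before use if made in the protocol (Protocol 13.2), and a check of admissions in about 10 patients. The SAE count may rise slightly.

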### **Treatment Emergent AEs**

A Treatment-emergent adverse event (TEAE) is defined as an event that emerges after the NVDX3 was implanted, having been absent pre-implant surgery, or worsens relative to the pre-implant state.

## **AE of Special Interest (AESI)**

The following adverse events will be considered as of special interest:

- Hypersensitivity reaction
- Immunological reaction
- An AE requiring immunosuppressive medication
- Ectopic bone formation
- Tumor formation
- Treatment failure:
  - Continued non-union/Non-fusion
  - Refracture of the targeted area
  - Revision surgery/intervention including removal of NVD-X3
  - Any other condition considered by the treating physician as treatment failure

## **Reportable AESI**

An AESI that is assessed by the PI as possibly, probably or definitely related to NVDX3 is defined as a reportable AESI (rAESI) and will be evaluated throughout the same process as a SAE ( see section 8.2.5)

## **AE classification**

### **a) Severity of the AE**

Severity of adverse events (AEs) is assessed as follows:

- **Grade 1 - Mild**; asymptomatic or mild symptoms; clinical or diagnostic observations only; intervention not indicated.
- **Grade 2 - Moderate**; minimal, local or noninvasive intervention indicated; limiting age-appropriate instrumental activities of daily living (ADL).
- **Grade 3 - Severe or medically significant but not immediately life-threatening**; hospitalization or prolongation of hospitalization indicated; disabling; limiting self-care ADL.
- **Grade 4 - Life-threatening consequences**; urgent intervention indicated.
- **Grade 5 - Death related to AE**.

**b) Relationship to the NVDX3 treatment**

All adverse events (AEs) must have their relationship to the NVDX3 treatment (relatedness to the NVDX3 implant, the NVDX3 implant procedure and other study or non-study related procedures) assessed by the Principal Investigator who examines and evaluates the patient based on the Investigator Brochure, the temporal relationship of the event and his/her clinical judgment. Alternative causes, such as underlying disease(s), concomitant therapy, and other risk factors will be considered and investigated. The degree of certainty about causality will be graded using the categories below.

For each AE/SAE, the Principal Investigator must document in the medical notes that he/she has reviewed the AE/SAE and has provided an assessment of causality.

There may be situations in which an SAE has occurred, and the Principal Investigator has minimal information to include in the initial report to the Sponsor. However, it is very important that the Principal Investigator always assesses the causality for every event before the initial transmission of the SAE data to the Sponsor. The Principal Investigator may change in the eCRF his/her opinion of causality in light of follow-up information: a SAE follow-up report with the updated causality assessment will be recorded in the eCRF.

As part of medical review, the causal relationship will also be assessed by the safety officer of the Sponsor or his delegate.

**c) Expectedness**

An SAE will be considered unexpected if the nature, severity, or frequency of the event is not consistent with the risk information previously described for NVDX3. The ‘expectedness’ of a serious adverse reaction (SAR) is assessed in the light of the reference safety information (RSI) included in the latest version of the approved Investigator Brochure.

## **8.2. Safety Reporting procedures**

### **8.2.1. Time period and frequency for collecting AE/SAE information**

All AEs and SAEs will be collected from the signing of the ICF until the (early) Termination Visit at the time points specified in the Schedule of Activities ([Section 6.1](#)).

Any medical condition that is present at the time of the patient’s screening will be considered as baseline and not reported as an AE. However, if the trial patient’s condition deteriorates at any time during the trial, it will be recorded as an AE.

Changes in the severity of an AE/SAE will be documented to allow an assessment of the duration of the event at each level of severity to be performed. AEs characterized as intermittent require documentation of onset and duration of each episode.

Investigators are not obliged to actively seek AE or SAE in patients after their final discharge from the study. However, if the Principal Investigator learns of any SAE, including a death, at any time after a patient has been discharged from the trial, and he/she considers the event to be reasonably related to NVDX3 or trial participation, the Principal Investigator must promptly notify the Sponsor or designee.

Prompt notification by the investigator to the sponsor of an SAE is essential so that legal obligations and ethical responsibilities towards the safety of participants and the safety of an IMP under clinical investigation are met.

#### **8.2.2. Detection of AE/SAE information**

AEs and SAEs may come to the attention of trial personnel during trial visits and interviews of the patient, his/her parent(s) and/or legal guardian(s) presenting for medical care, or upon review by a trial monitor.

Care will be taken not to introduce bias when detecting AEs and/or SAEs. Open-ended and non-leading verbal questioning of the patient is the preferred method to inquire about AE occurrences.

#### **8.2.3. Follow-up of AE/SAE information**

After the initial AE/SAE report, the investigator is required to proactively follow each participant at subsequent visits/contacts.

All SAEs, and non-serious related AEs (excluding unlike related events) will be followed until resolution, stabilization, the investigator determines that it is no longer clinically significant, the event is otherwise explained, or the participant is lost to follow-up.

#### **8.2.4. Adverse Event reporting**

When an AE occurs, the Principal Investigator, or defined delegate(s), will review all documentation (e.g., hospital progress notes, laboratory reports, and diagnostics reports) related to the event and record all relevant AE information in the eCRF.

**All AEs including local and systemic reactions not meeting the criteria for SAEs will be captured on the case report form (eCRF) within 5 working days of event awareness.**

Information to be collected includes event description, time of onset, investigator's assessment of severity, relationship to surgical procedures and trial product (assessed only by those with the training and authority to make a diagnosis), and time of resolution/stabilization of the event.

AEs occurring while on trial must be documented appropriately regardless of relationship.

#### **8.2.5. Serious Adverse Event and reportable AESI reporting**

The Principal Investigator is responsible to report to the Sponsor, all SAEs and reportable AESI (rAESI) within 24 hours after obtaining knowledge of the event, whether or not considered trial treatment related.

SAE and rAESI will be reported electronically through completion of the electronic safety form (eCRF).

Note: An Initial notification via telephone does not replace the need for the investigator to complete and sign the safety CRF pages

Other supporting documentation of the event may be requested by the Sponsor or designee and should be provided as soon as possible. Hospital or patient records, attached to the safety form, need to be anonymized and proper identification (patient number) needs to replace the identifiers.

**All SAEs/rAESIs and updated SAE/rAESI data will be recorded and reported to the Sponsor, or designee, within 24 hours after obtaining knowledge of the event or updated information**

After the trial is completed at a given site, the electronic data collection tool will be taken off-line to prevent the entry of new data or changes to existing data. If a site staff receives information about a new safety from a trial patient or receives updated data on a previously reported SAE /rAESI after the electronic data collection tool has been taken off-line, the site can report this information to the Sponsor or designee on a paper safety form.

### **8.3. Study Halting rules**

As a consequent to the nature of the product, implanted through a single administration surgical intervention, study halting rules will **only be applicable during the period between the first patient implant and last patient implant surgery visit. After completion of the last implant surgery, no more new patients will be added, and all implanted patients will need to be followed for safety for the whole study period.**

During this period, important safety events resulting from any study procedure, including NVDX3 implant surgery, may temporarily suspend or prematurely terminate any planned surgical interventions or new study enrolment.

Written notification, documenting the reason for trial suspension or termination, will be provided by the suspending, or terminating party to investigators, the Sponsor and regulatory authorities. Halting the study will allow time to review the safety concerns with CA/IEC and consider if is possible to construct a path forward. Trial may resume once concerns about safety, protocol compliance, and data quality are addressed, and satisfy the IEC and/or regulatory authorities.

If the trial is prematurely terminated or suspended, the Principal Investigator will promptly inform the patients, the IEC, and the Sponsor will provide the reason(s) for the termination or suspension to the regulatory authorities. The parent(s) or the legal guardian(s) of the patient will be contacted, as applicable, and be informed of changes to trial visit schedule.

If an event, corresponding to the above-mentioned study halting rules, occurs beyond the above-mentioned period the study will not be halted as all 10 recruited patients have been implanted with NVDX3 and continued safety surveillance must be guaranteed. All concerned parties will be notified promptly in accordance with the drug safety reporting requirements, allowing proper review evaluation of the events and eventually decide on the path forward in the best interest of the patient.

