## PROTOCOL SYNOPSIS

**Title:** A first-in-human proof-of-concept (PoC) study with NVDX3, an osteogenic implant of human allogenic origin, in the treatment of distal radius fractures in adults.

**Study description:** A single arm, monocentric study in adult patients, suffering from a distal radius fracture, treated during the osteosynthesis intervention with NVDX3.

After the Implant Surgery (IS) the safety follow-up will cover two distinct stages followed by a long-term safety follow-up study:

- Phase 1: Acute safety phase up to 6 weeks post-IS (W6)
- Phase 2: Long-term safety follow-up from W6 up to of 12-month post-IS
- NVDX3-CLN0X: NVDX3 long-term safety study up to 10 years post-NVDX3-CLN01 study

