**Description of Study Treatment:**

NVDX3 is an osteogenic implant of human allogenic origin. This lyophilized and sterilized tissue engineered product is composed of extracellular matrix, biologically active growth factors and biomolecules, non-viable osteogenic cells associated with hydroxyapatite/beta-tricalcium phosphate (HA/TCP) particles. NVDX3 is formulated as a lyophilized powder, sterilized by gamma radiation.

NVD-X3 off-the-shelf implant is intended to induce bone formation between two bone segments [REDACTED] As well in an orthotopic as in a heterotopic environment.

[figure not shown]
**Study Duration:** **Protocol NVDX3-CLN01:** Approximately 15 months. (From FPFV to LPLV)

**Protocol NVDX3-CLN0X:** Up to 10 years after the LPLV in the NVDX3-CLN01 study

**Patient Duration:** **Protocol NVDX3-CLN01:** Approximately 13 months (From DRF diagnosis to the 12-months post-implant surgery)

**Protocol NVDX3-CLN0X:** Up to 10 years after the patient's last visit in the NVDX3-CLN01 study

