#### Risks related to the study product:

Pre-clinical in vitro and in vivo studies on safety, mutagenicity, tumourigenicity, immunotoxicity and immunogenicity support that NVDX3 is safe, non tumourigenic and has very low to no immunogenic potential. No NVDX3 related side effects have been observed during the pre-clinical development. For any updates on observed risks related to NVDX3, please refer to the latest version of the Investigators Brochure (IB)

Despite the positive safety profile set during pre-clinical development, the following events cannot formally be excluded due to the allogeneic and the ATMP nature of the product (ref. recommendations of the CHMP “Guideline on safety and efficacy follow-up- Risk management of advanced therapy medicinal products – EMEA/149995/2008”):

1. Immune reactions including but not limited to fever, local or systemic allergic reactions, redness of the skin, implant site infection and graft rejection. Immunogenic site effects will receive special attention and will be followed closely through safety lab analyses up to 6 months post-grafting surgery.

2. Due to a detection limit of the applied analytical methods, the presence of viable donor cells and related potential abnormal activity cannot completely be ruled out. This will be closely evaluated radiologically and clinically at each follow-up visit of this study and during the long-term safety study (NVDX3-CLN0X).

Other historically reported risks related to ATMPs (but not observed for NVDX3) defined within the recommendations of the CHMP (“Guideline on safety and efficacy follow-up- Risk management of advanced therapy medicinal products – EMEA/149995/2008”), have been addressed more in detail in the latest version of the IB.

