## 3. STUDY DESIGN AND ENDPOINTS

### 3.1. Description of the study design

This is a prospective, single arm, monocentric first-in-human PoC study in adult patients, suffering from a distal radius fracture, treated during the surgical intervention with NVDX3, an osteogenic implant from human allogeneic origin.

As per standard of care, patients with DRF are followed up to 3 months post-intervention. In the context of this trial, patient safety and IMP efficacy will be followed up to 12 months post-implant surgery.

At the end of this study, the included patients will be invited to participate in a long-term safety follow-up study for an additional period of 10 years.

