## Exploratory endpoints

## 4. STUDY ENROLLMENT AND WITHDRAWAL

### 4.1. Inclusion criteria

Patients must meet all the inclusion criteria to be eligible to participate in the study:

1. Male or female patients within the age range of  $\geq 18$  years to  $\leq 80$  years.
2. Patient diagnosed with DRF **with confirmed**:
  - a. Classification AO/ATO: C2 and C3 - Intra-articular & multifragmentation.
  - b. Estimated volume of the targeted bone void should not exceed 5cc.
  - c. Availability of diagnostic AP and LAT X-ray or CT scan.
3. Patient can undergo the targeted surgical intervention within 7 days post-DRF diagnosis.
4. Patient fulfills criteria for undergoing a surgical intervention.
5. Patient has understood and accepted to participate in the study according to all study procedures by signing the informed consent.

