#### **4.3. Strategy for recruitment and retention**

It is intended to enroll 10 evaluable patients. A patient is considered evaluable once he/she underwent the implant surgery with NVDX3. Non-evaluable patients will be replaced.

No specific recruitment activities are envisioned.

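### The visible protocol and SAP neither space the first-in-human NVDX3 implants nor require earlier patients' safety data to be reviewed before the next implant

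*Protocol*

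**What the plan says.** Protocol 3.1 describes the design: "This is a prospective, single arm, monocentric first-in-human PoC study in adult patients". Section 4.3 adds: "It is intended to enroll 10 evaluable patients". It provides for replacing patients who are not implanted but says nothing about order or spacing. The only timing condition on surgery concerns the patient's own injury (4.1): "Patient can undergo the targeted surgical intervention within 7 days post-DRF diagnosis".

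Section 8.3 states that, between the first and last implant, "important safety events resulting from any study procedure, including NVDX3 implant surgery, may temporarily suspend or prematurely terminate any planned surgical interventions"; new enrolment may be stopped too. Section 4.6 says that 8.3 sets out the number, nature and/or severity of events that trigger suspension, but no such list is visible in 8.3. Section 9.4.6 makes patient-by-patient and interim analyses optional. The SAP has no rule on sequence or review.

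Safety data are collected early. Laboratory tests and skin inspection take place at discharge, W2 (V4) and W6 (V5) (6.1). The local radiologist completes a questionnaire at each imaging visit (8.1.6), and the Principal Investigator assesses causality for every adverse event (8.1.7). SAEs and reportable AESIs go to the sponsor within 24 hours (8.2.5). Other adverse events must be in the eCRF within 5 working days (8.2.4).

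Some text cannot be seen. Sections 8.4 and 6.1.4 refer to a Safety Monitoring Plan that was not supplied, the trial design scheme is missing, and 5.1.4 and 5.1.5 are redacted or blank.

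**The concern.** Section 1.2.1 names, among events that cannot formally be excluded, "Immune reactions including but not limited to fever, local or systemic allergic reactions, redness of the skin, implant site infection and graft rejection". A halt protects only patients who have not yet been implanted, so its value depends on someone looking at the earlier patients in time. The plan gathers the relevant data at discharge, W2 and W6, but no visible text ties any of it to the decision to operate on the next patient. Whether it is read before the next implant is left to discretion.

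**Working it through.** The plan states no accrual rate and has no figure of its own to reproduce, so the size rests on an assumed accrual window.

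**Inputs.** Study duration is about 15 months and patient duration about 13 months, including 12 months after surgery (synopsis). There are 10 implants (4.3). V4 is at day 13 ± 2 and V5 at day 42 ± 7 (6.1).

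**Window W.** 15 − 13 = 2 months (about 60 days) to 15 − 12 = 3 months (about 90 days). With even spacing the gap is W/9, which is 6.7 or 10.0 days.

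**Patients implanted before the first patient reaches a visit** (counting that patient):

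| | W = 60 | W = 90 |
|---|---|---|
| before V4 (day 13) | 2 | 2 |
| before V5 (day 42) | 7 | 5 |

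Both durations are approximate. Taking the study as 14.5 to 15.5 months and patient time as 330 days (lower V8 window) to 13.5 months gives W = 30 to 142 days, and ranges of 1 to 4 before V4 and 3 to 10 before V5. If the eight middle implants instead fall at random, the count before V5 is 1 + Binomial(8, 42/W): mean 1 + 8 × 0.70 = 6.6 or 1 + 8 × 0.467 = 4.7, with 80% ranges 5–8 and 3–7.

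**Data available for a review.** A patient's V4 is complete by the second implant after their own (2 × 6.7 = 13.3 days, or 20 days, against day 13). So at implants 3 to 10, V4 data exist from 1 to 8 earlier patients. The margin at W = 60 is thin. With V4 on day 15 it becomes 1 to 7 patients at implants 4 to 10.

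**Later patients protected** if a problem is first recognised at a given visit of patient 1, 2, ..., averaged over which of the ten is affected:

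| Recognised at | No hold | V4 hold | V5 hold |
|---|---|---|---|
| V4, either W | 8, 7, ..., 1, 0, 0: 36/10 = 3.6 | 9, 7, ..., 1, 0, 0: 3.7 | 3.7 |
| V5, W = 60 | 3, 2, 1, 0, ...: 0.6 | 4, 2, 1, 0, ...: 0.7 | 9, 2, 1, 0, ...: 1.2 |
| V5, W = 90 | 5, 4, 3, 2, 1, 0, ...: 1.5 | 6, 4, 3, 2, 1, 0, ...: 1.6 | 9, 4, 3, 2, 1, 0, ...: 1.9 |

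A hold changes only the patient 1 entry. With V4 on day 15 and W = 60, the V4 row becomes 28/10 = 2.8 without a hold and (9 + 21)/10 = 3.0 with one.

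**Cost of a hold.** Added time is the hold day minus one gap. For V4 this is 13 − 6.7 = 6.3 or 13 − 10 = 3.0 days (8.3 or 5.0 if V4 is on day 15). For V5 it is 35.3 or 32.0 days. Fractures arriving during a V4 hold number 1 with even spacing, 2 with V4 on day 15 and W = 60, and 8 × 13/W = 1.7 or 1.2 with random arrivals. With W = 30 there are 3. A V5 hold would meet 6 or 4.

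**The case against.** The strongest objection is that absence cannot be shown. Safety process and timelines are assigned to a document that was not supplied, and other places that could carry a rule are missing or redacted. This stands: the point is first a question to the sponsor and cannot be read as proof that no rule exists.

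A reader might also infer that an immune reaction could wait a week before the sponsor hears of it, longer than the 6.7-day gap between implants. The documents do not support that. Hypersensitivity and immunological reactions are AESIs, and if judged at least possibly related to NVDX3 they are reported within 24 hours (8.1.7, 8.2.5). The 5-working-day limit, about 7 calendar days, applies to other non-serious events, such as a non-serious implant site infection. It governs eCRF entry. At a single centre the surgical team would probably know already, so the delay matters mainly for sponsor awareness, or if the second site allowed by 9.6 is used. With 90-day accrual the gap is 10 days in any case.

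The product is sterilised, its cells are described as non-viable, it is given once, and no preclinical safety signal was seen. Spacing is therefore a judgement, and no text in the documents makes it obligatory. Still, 1.2.1 itself says that viable donor cells and immune reactions cannot be fully excluded, and reviewing data already in hand costs little.

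**Conclusion.** In the visible text, nothing spaces the implants or makes review of earlier patients a condition of the next one. That finding does not depend on any accrual assumption; its size does. Under even accrual over 60 to 90 days, W2 data from up to eight earlier patients would be available but need not be read, and 5 to 7 of 10 patients would be implanted before the first completes the acute phase.

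Those counts might suggest that a long hold after the first patient is needed. The figures do not support that as the default. A V4 hold raises the mean number protected by about 0.1 (0.2 with V4 on day 15 and 60-day accrual), and any hold helps only if the first patient is the one affected. All these gains are upper bounds, because existing reporting may catch the same events. The value lies mainly in the required review. Confidence is medium because the Safety Monitoring Plan was not available.

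**What to change.** Ask the sponsor whether the Safety Monitoring Plan or another unseen section already sets such a rule. If so, cite it in 8.3. If not, state in 4.3 and 8.3:

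- (a) Before each implant, the investigator and sponsor document a review of all available safety data (adverse events, laboratory tests, skin inspection, local radiology questionnaire) from every patient already implanted, across sites if a second is used.
- (b) The second implant waits until the first patient's V4 safety data have been reviewed, and no two implants take place on the same day.

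The cost is amendment wording and nine short reviews (before implants 2 to 10), with no new visits or tests. The hold adds about 3 to 8 days, so the study stays at about 15 months. About 1 to 2 eligible fractures may be lost (up to 3 if accrual takes only 30 days). The 7-day surgery limit may rescue some of these, but a review not finished within it would lose that patient. A V5 hold is a stricter trade-off: about 32 to 35 days and 4 to 6 fractures.

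SAP 3.6 reports imaging already taken during surgery, so the change can protect only patients not yet implanted. If all ten have been, list in the CSR each implant date and how many earlier patients had completed V4 and V5 by then. Visit dates are already collected (SAP 2.6.1), so this costs almost nothing.
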